3 OVERALL DESIGN AND PLAN OF THE STUDY

3.1 Summary of Study Design

This is a multicentre, randomised, double-blind, Phase II, parallel group comparison study of the efficacy and safety of FP-1201-lyo compared to placebo in patients surviving emergency open surgery for an infra-renal ruptured abdominal aortic aneurysm. Both treatment groups will receive standard supportive care.

With an estimated screening failure rate of approximately 15%, maximum of 180 patients will be consented and entered into the study in order to randomise and initiate treatment of 152 patients. The sample size calculations will be re-evaluated after the first interim analysis has been performed.

The study design incorporates an Independent Data Monitoring Committee (IDMC) that will review safety data retrieved for interim analysis (i.e. Adverse Events [AE] and Serious Adverse Events [SAE]). Details of the IDMC are given in Section 9.8.

[figure not shown]
Patients will receive 10 µg FP-1201-lyo or placebo intravenously as a bolus injection once every 24 hours. The maximum duration of treatment will be 6 days. Treatment may be discontinued before 6 days if the patient's condition improves beyond the need for ICU treatment and if, in the opinion of the Investigator, the patient would likely not benefit from continuation of treatment.

A schedule for the tests and assessments to be conducted during this study is found in the Tables 5-8.

The study objectives and outcome measures to be used in this study are described in Sections 2 and 6.

The study design is summarised below in Figure 1.

Figure 1: Flow Diagram of Study Design

3.2 **Criteria for the Study assessments**

3.2.1 **Primary Efficacy Endpoint:**

- All-cause mortality at D30

Secondary Efficacy Endpoints:

- All-cause mortality at D90 (3 months)
- Number of ventilator free days (VFDs) at D30
- Number of days receiving hemodialysis at D30 and D90
- Number of organ failure free days up to D30 by means of the SOFA score
- Prevalence of abdominal compartment syndrome, i.e. intra-abdominal pressure (IAP) between study groups
- Neutralizing antibodies against IFN beta-1a (NAbs) in whole blood samples up to D30
- Disability at D90 (3 months) by modified ranking scale.

3.2.2 **Safety**

- Clinically significant treatment emergent adverse events (TEAEs) up to D30 from vital signs data, laboratory data, physical examinations and spontaneous reporting when conscious

3.2.3 **Pharmacoeconomics assessments**

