4.4.1.1 Non-attendance of Follow-up Assessments

Attempts should be made to contact patients discharged from hospital who do not attend their study follow-up assessments to ensure their well-being. In such cases, the

patient will be contacted at least twice by telephone and once by letter to request that they attend the scheduled follow-up assessment. If patients do not respond they will be considered as *lost to follow up* at that time point. If a patient is lost to follow-up, wherever possible mortality data will be sought at all remaining mortality time points from alternative sources such as the patient's local physician.

4.4.2 **Replacement Policy**

All patients who become ineligible after consenting but before randomisation are replaced and deemed as screening failures. A screening failure is defined as any patient who does not comply with the inclusion and exclusion criteria during screening **or** prior to randomisation and receiving the first dose of study medication.

Patients who complete screening and are randomised and receive at least 1 dose of the study medication will not be replaced even if later withdrawn or lost to follow up.

4.5 **Planned Sample Size and Number of Study Centres**

It is planned to randomise 152 patients at 10-18 hospital study centres in Finland, in UK, in Lithuania and in Estonia and possibly in other countries in EEA and in USA for this study. Possible additional selection will be decided later, as required. See Section 8.2. for a discussion of sample size.

4.6 **Patient Randomisation**

4.6.1 **Randomisation Scheme**

Patients are randomly assigned to treatment with FP-1201-lyo or placebo in the randomisation ratio of 2:1 (active:placebo) for treatment groups, stratified by sex and age.

The treatment assigned to each patient is determined according to a computer-generated randomisation list within eCRF.

4.6.2 **Randomisation of Patients to Treatment**

Randomisation of patients to treatment will occur immediately after completion of surgery and after all screening procedures have been performed and eligibility for inclusion in the study has been confirmed. Each randomised patient will receive a unique randomisation number. Randomised patients who terminate their study participation for any reason, regardless of whether study drug was taken or not, will retain their randomisation number.

The Investigator will use IWRS for randomisation of patients. Details can be found in the study file.

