6.2.6 Days in hospital and/or other health care unit

The length of a patient's hospital stay will be assessed by:

- the number of days the patient stayed in hospital at D30 and D90
- the number of days the patient stayed at another primary or rehabilitating health care unit after hospital discharge at D30 and D90.

6.2.7 *Days on haemodialysis*

The number of days on haemodialysis will be assessed at D30 and D90. Haemodialysis at D90 is considered permanent.

6.2.8 *Prevalence of compartment syndrome as measured by intra-abdominal pressure (IAP)*

Intra-abdominal pressure (IAP) is routinely measured during ICU stay via urine bladder catheter. IAP is recorded daily and a comparison of IAP between study groups is made.

6.3 **Safety Variables**

6.3.1 *Adverse Events*

6.3.1.1 *Collection of Adverse Events*

It is the responsibility of the Investigator to collect all AEs (both serious and non-serious) derived by observation, by spontaneous unsolicited reports of patients, and, where appropriate, by routine open questioning, e.g., “How have you felt since I last saw you?”

6.3.1.2 *Definitions*

Definitions of AEs and SAEs and their documentation and reporting within this study follow International Conference on Harmonisation (ICH) Good Clinical Practice, European Union, and national regulations and requirements (Clinical safety data management 1994).

An AE is defined as any untoward medical occurrence that occurs in a patient or clinical investigation subject administered a pharmaceutical product, and which does not necessarily have to have a causal relationship with this treatment. An AE can therefore be any unfavourable and unintended sign (including an abnormal laboratory finding), symptom or disease temporally associated with the use of an investigational product, whether or not it is considered related to the product.

All AEs up to D30 are collected. All AEs up to D30, which lead to death, are reported as SAEs. However, all deaths up to D90 will be reported as SAEs. Concomitant illnesses, which existed before entry into the study, will not be considered AEs unless there is any deterioration from baseline that is considered clinically relevant or significant during treatment or follow-up period until D30 or discharge from ICU. All AEs must be documented, regardless of the source of identification (e.g., physical examination, laboratory assessment, ECG, reported by patient).

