7.5.1 Schedule of assessments for D0 to D5

Day 0 0 hrs and post dose:

The first dose of study medication will be administered on D0 at 0 hrs (with maximum of 4 hours after the RAAA surgery). The following D0 study medication administration procedures and post dose assessments are performed (refer to Table 5) and the data is recorded in the eCRF:

- Administration of study medication: FP-1201-lyo or placebo, administered as a bolus intravenous injection, followed by a 5 ml flush of sterile saline
- SOFA score assessment for baseline
- Recording of concomitant medications and therapies
- AE reporting commences after the consent has been obtained.

Day 1 to Day 5:

From D1 to D5 inclusive, the following study assessments and procedures will be performed (patient will not be subjected for additional invasive assessments if not standard for patient care in ICU/hospital ward):

- Check if patient is on ventilation (refer to VFD definition in Section 6.2.3)
- Check if patient is in the ICU

- Check if patient is on organ support
- The number of organ failure free days by means of SOFA. SOFA scores are assessed daily in the ICU (refer to Table 1 and Table 8 for the SOFA composition and schedules. **Note:** The worst daily value of each element should be used to calculate the overall SOFA score.
- Vital signs (temperature, BP and HR) must be measured and recorded between 6 am to 10 am using the values closest to 8 am (assuming these values are representative of the patient's condition). All vital signs assessments must be made at the same time point when possible.
- Blood biochemistry: samples must be taken between 6 am to 10 am (refer to Section 6.3.2. for specific biochemistry variables)
- Haematology: samples must be taken between 6 am to 10 am (refer to Section 6.3.2. for specific haematology variables)
- Intra-abdominal pressure (IAP) must be measured daily between 6 am to 10 am during ICU stay or until complete resolution of elevated pressure. Not applicable if abdomen was left open at index operation
- Daily recording of major surgical outcomes affecting patient
 - open abdomen: yes/no (to detect time of closure or re-opening)
 - lower limb embolization (yes/no), consequent rhabdomyolysis (yes/no)
 - Explorative laparotomy for bleeding (yes/no), record blood loss
 - Explorative laparotomy and bowel resection (yes/no)

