Patients will receive 10 µg FP-1201-lyo or placebo intravenously as a bolus injection once every 24 hours. The maximum duration of treatment will be 6 days. Treatment may be discontinued before 6 days if the patient's condition improves beyond the need for ICU treatment and if, in the opinion of the Investigator, the patient would likely not benefit from continuation of treatment.

With an estimated screening failure rate of approximately 15%, a maximum of 180 patients were planned to be consented and entered into the study in order to randomise and initiate treatment of 152 patients.

Study was discontinued after an Interim analysis.

5 Study variables

The following variables will be evaluated

The demographic and baseline variables

Gender, age at entry, race, weight (predicted or actual), height, medical history, concomitant medications/therapies, major surgical outcomes affecting patient and pregnancy test (females of child bearing potential, and peri procedural information (duration of the surgical procedure for RAAA, total clamping time, total bleeding volume, total volume substitution, total blood substitution, total red blood cells substitution, total platelets substitution, total crystalloids substitution and total diuresis volume during procedure and recycling of blood during surgery (yes/no)).

The primary efficacy outcome variable

- All-cause mortality at D30

The secondary efficacy outcome variables

- All-cause mortality at D90 (3 months)
- Number of ventilator free days (VFDs) at D30
- Number of days receiving haemodialysis at D30 and D90
- Number of organ failure free days up to D30 by means of the SOFA score
- Prevalence of abdominal compartment syndrome, i.e. intra-abdominal pressure (IAP) between treatment groups
- Neutralizing antibodies against IFN beta (NAbs) in whole blood samples up to D30

- Disability on D90 measured by modified ranking scale (mRS)

Safety variables

Adverse events, vital signs (body temperature, blood pressure, heart rate), physical examination and clinical laboratory parameters (biochemistry and haematology).

Pharmacodynamic (PD) and tentative disease specific marker variables

- MxA (protein) concentration in whole blood samples from baseline up to D13
- CD73 concentration in serum samples from baseline up to D6
- Potential Inflammatory Markers (IL-6 and HGF) in serum samples from baseline up to D13

Pharmacoeconomic variables

- Length of ICU stay, in terms of ICU free days at D30

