12.2 Secondary efficacy variables

The following secondary endpoints will be analysed:

- Time and reason/diagnosis of death up to D90 (3 months)
- Number of VFDs up to D30
- Number of days receiving hemodialysis at D30*
- Number of ICU free days up to D30*
- Organ failure free days up to D30
- Number of days in hospital up to D30 (length of stay in another health care facility)*
- Prevalence of abdominal compartment syndrome, i.e. intra-abdominal pressure (IAP) value differences between study groups
- Disability on D90 measured by modified ranking scale (mRS)
- Neutralizing (and anti-drug) antibodies IFN beta (ADAs and NAbs) in whole blood samples up to D30

*ICU free days and number of days in hospital, length of stay in another health care facility and number of days receiving hemodialysis at D90 summarized in pharmacoeconomic tables

All-cause mortality at D90 (3 months) will be compared using Cox regression model including stratification factors (if feasible). Estimated hazard ratios will be presented with associated 95% CIs and log-rank p-values for the FAS-E. Also, similar logistic regression as for the primary endpoint (D30 mortality) will be done.

For endpoints number of VFDs, number of ICU free days, organ failure-free days, number of days on hemodialysis, number of days in hospital, length of stay in another health care facility and IAP values, data will be summarised in terms of the mean, median, minimum and maximum, and the treatment groups will be compared using the Mann-Whitney U-test. Descriptive tables of IAP grade by timepoint will be presented using counts and percentages. Number of days on hemodialysis, number of days in hospital, length of stay in another health care facility and IAP value analyses will be performed for all patients and excluding deaths separately.

Complete data on organ failure free days may be unavailable due to SOFA scores not being assessed after ICU treatment. To account for this, the number of organ failure free days will be analysed by expressing these as a proportion of the days on which SOFA scores are available.

Disability measured with mRS will be summarized descriptively and the treatment groups will be compared using the Cochran-Mantel-Haenszel test for trend.

ADAs and NABs in whole blood samples up to D30 will be summarized using descriptive statistics.

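### Abdominal compartment syndrome is named as a prevalence but analysed as daily pressures, with no per-patient proportion, case definition or grade cut-off, and the later daily contrasts are selected on post-dose course

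*Protocol*

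**What the plan says.** - **Endpoint.** Protocol 3.2.1 lists "Prevalence of abdominal compartment syndrome, i.e. intra-abdominal pressure (IAP) between study groups". SAP section 5 has the same item: "Prevalence of abdominal compartment syndrome, i.e. intra-abdominal pressure (IAP) between treatment groups".
- **Measurement.** Protocol 6.2.8 says "IAP is recorded daily and a comparison of IAP between study groups is made". For D1 to D5, Protocol 7.5.1 says IAP "must be measured daily between 6 am to 10 am during ICU stay or until complete resolution of elevated pressure", and adds "Not applicable if abdomen was left open at index operation". Protocol 7.5.2 repeats the ICU and resolution rule for D6 to D30 without the open-abdomen sentence. A footnote to Table 7 limits the IAP reading at discharge to patients still in ICU.
- **Analysis.** Protocol 8.5.2 and SAP 12.2 restate the endpoint as differences in IAP values and assign the Mann-Whitney U-test. The SAP adds: "Descriptive tables of IAP grade by timepoint will be presented using counts and percentages". SAP 9.2 rules out imputation.
- **Deaths.** SAP 12.2 repeats the IAP value analysis without patients who died. The matching table titles in SAP 19.3 leave out only early deaths.
- **Related data.** Protocol 7.5.1 has sites record daily "open abdomen: yes/no (to detect time of closure or re-opening").

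**The concern.** A prevalence is a share of patients. Daily pressures, and daily grade percentages among those measured, do not give one. The same patient can appear on several days and the denominator changes each day, so daily counts cannot be added up to the number of patients ever affected.

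The by-day comparisons are also not protected by randomisation after the first days. A patient contributes on a given day only if alive, and in ICU or with pressure not yet resolved. If the drug changes length of ICU stay or survival, and milder patients leave ICU sooner, the two measured groups differ in severity for reasons unrelated to any effect on pressure. The named question would then go unanswered, and a late-day p-value could reflect who was left to measure.

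**Working it through.** **1. What a per-patient proportion needs.** It needs a case definition, a pressure or grade threshold, a time window and a denominator. Protocol 3.2.1, 6.2.8, 7.5.1, 7.5.2 and 8.5.2 and SAP 5, 12.2 and 19.3 supply none of these. In SAP 19.3, Tables 14.2.1.12.1 to 14.2.1.13.4 are all by time point, and no table has the patient as its unit. SAP 12.2 does not say whether the Mann-Whitney test is run at each time point. The table titles suggest that it is, and the checks below assume so.

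**2. Which selection is post-dose.** Protocol 4.6.2 states "Randomisation of patients to treatment will occur immediately after completion of surgery", so an abdomen left open at the index operation is a baseline state. ICU discharge, resolution of pressure, death and later re-opening all come after the first dose.

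**3. Model A: a true benefit.** The documents give no IAP mean, SD or ICU stay, so all parameters are assumed.

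- IAP = 14 + 4 × severity − 0.3 × day + noise (SD 2). Severity has SD 1 and is 0.5 lower on active, so the true difference is 4 × 0.5 = 2.0 mmHg.
- log(ICU stay) = log 5 + b × severity + noise (SD 0.4). The placebo median is 5 days. With b = 0.5 the active median is 5 × exp(−0.25) = 3.9 days.

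Difference among patients still in ICU (mmHg):

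| b | D3 | D5 |
|---|---|---|
| 0 | 2.0 | 2.0 |
| 0.2 | 1.9 | 1.7 |
| 0.5 | 1.4 | 1.2 |

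With b = 0.5 the difference is 1.9 on D1, when 98 to 99% are measured, and 1.0 on D9. On D5, 50% of placebo and 35% of active patients are measured. The D5 loss is therefore 0, 0.3 or 0.8 mmHg for the three values of b.

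**4. Model B: no effect on IAP.** IAP = 13 + 3 × severity + noise (SD 2), 20% open at index, median ICU stay 5 days, and stay related to severity with slope 0.5 unless stated. D30 mortality is 37% and 15%, from the sample-size assumptions. The arms are the planned 86 and 43. The ratio of active to placebo ICU stay is varied.

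| Stay ratio | D5 measured, active / placebo | D5 spurious difference (active − placebo) | Rejection, D3 / D5 |
|---|---|---|---|
| 1.0 | 39% / 35% | +0.1 mmHg | 5% / 5% |
| 0.85 | 31% / 35% | +0.5 | 7% / 8% |
| 0.7 | 22% / 35% | +1.0 | 14% / 14% |
| 0.5 | 11% / 35% | +1.9 | 40% / 29% |

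With ratio 0.7 but stay unrelated to severity, the D5 difference is +0.1 mmHg and rejection is 4%. With equal stay and equal mortality, so that only the index open-abdomen rule acts, rejection is 5 to 6%: that rule alone adds no bias.

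At 35 evaluable patients (assumed split 23 and 12) and ratio 0.7, the D5 bias is +0.9 mmHg but rejection stays near 5%. The D5 groups would be about 0.22 × 23 = 5 and 0.35 × 12 = 4 patients.

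**5. Does a per-patient worst value help?** In Model A with no drug effect on IAP, b = 0.5 and active stay at 0.7 of placebo, daily means are off by 0.9 (D3) to 1.4 mmHg (D9) against active. The mean per-patient peak is off by only about 0.15 to 0.3 mmHg, depending on b, in favour of active because fewer days are observed. With every patient in the denominator, the share above an arbitrary 20 mmHg, used only for illustration, is 15.0% on placebo and 14.3% on active.

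Neither model includes the stop at resolution or re-opening, and Model A has no deaths.

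**The case against.** The best defence is that the documents define the endpoint as they analyse it. They equate prevalence with IAP, Protocol 6.2.8 promises a comparison of IAP, and Protocol 8.5.2 already speaks of value differences. A reader might infer that the SAP silently swapped the endpoint. It did not, because the protocol had already done so. What stands is that the name and the analysis do not match.

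Four other strong readings are tempting and are not supported:

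- **No prevalence of any kind is produced.** Daily grade percentages are planned, and each is a point prevalence among those measured. What is missing is the per-patient figure and the meaning of the grades.
- **The open-abdomen rule biases the comparison.** It acts on a state fixed before allocation.
- **Only closed abdomens are ever measured, and only in ICU.** Re-opened abdomens are not expressly excluded, and the wording on resolution can be read as running past ICU discharge.
- **The plan hides a drug benefit.** In Model A the direction is kept on every day examined, D1 is nearly intact, and the loss vanishes when stay is unrelated to severity.

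It is also fair to say that a worst grade depends on days observed and on survival. It reduces the selection problem without removing it, and it can carry a small bias where the daily means carry none.

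**Conclusion.** The concern holds in a limited form. That the plan yields no per-patient proportion, case definition or grade cut-off follows from the text and needs no model. That later daily contrasts are conditioned on post-dose events also follows from the text.

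The size of the resulting bias cannot be read from the documents. Across the assumed scenarios it runs from nothing to 0.8 mmHg of a true 2.0 mmHg on D5, or from about 0 to 1.9 mmHg when there is no effect. It requires arms that differ in ICU stay or survival, with stay or survival related to severity.

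The priority is low. SAP 12.2 treats secondary endpoints as supportive without multiplicity adjustment, the trial was discontinued, and at about 35 evaluable patients the false-positive rate in the central scenario stays near 5%. The gain is mainly a readable answer to the endpoint as named.

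**What to change.** In SAP 12.2 and the table plan in SAP 19.3:

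1. Add one per-patient outcome: the worst IAP grade from D1 to ICU discharge. Write the grade cut-offs and the case threshold into the SAP before database lock. Because Protocol 5.4 has the code opened for the interim, record that they were set without sight of IAP by arm.
2. Use all FAS-E patients with the abdomen closed at index as denominator. Report n/N per arm with a risk difference and CI, plus a trend test across grades of the kind already planned for mRS.
3. Show re-opened abdomen, death before ICU discharge and no IAP value as separate rows, and index open abdomen as a row outside the denominator. State whether a re-opened patient keeps the grade recorded beforehand.
4. Keep the by-day value and grade tables as descriptive.
5. Reconcile the open-abdomen sentence in Protocol 7.5.1 with its absence from 7.5.2. Reconcile the exclusion of all deaths in SAP 12.2 with the exclusion of early deaths in the table titles. FAS-E already leaves out deaths within 36 hours, so if early death means the same there, those FAS-E tables repeat the main ones.

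The cost is one derived variable, one table and a few lines of definition, all from data already collected. The remaining weakness is the slight dependence of a worst grade on days observed; the separate rows let a reader judge it.
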